4.0 Methods

4.1 Design

This will be a randomized two arm trial to evaluate the feasibility and acceptability (attrition), and effect size of a bio-behavioral, two-component intervention to improve vulvovaginal atrophy and self-image and libido. We will also evaluate the sensitivity and effect size of the chosen outcome measures to determine the best primary outcome for a larger, well powered randomized clinical trial.

4.2 Subject Recruitment

Recruitment and screening: Potential participants from the community will be identified in three ways: (1) physician referrals; (2) ResearchMatch.org; and (3) study advertisements including social media campaign, radio ads, flyers/brochures and a study website. Flyers may be posted in the greater Knoxville area. Locations such as churches, gyms, and cancer support groups. Brochures and flyers may be provided to physicians, providers, and organizations to distribute. IRB-approved recruitment materials may be posted on social media or in University of Tennessee/non-University of Tennessee newspapers, newsletters or websites, or read over WUOT. Participant eligibility will be determined using the Screening Eligibility Check List created from the criteria listed in 4.3.

Baseline visit: If a woman is screened eligible using the screening eligibility checklist, she will be mailed or emailed the consent form and scheduled for a virtual baseline visit. Baseline visits will be conducted using a HIPAA compliant platform (video or phone). The purpose of the baseline visit is to ensure that participants understand the study requirements, have their questions answered, be consented, complete baseline questionnaires, and are randomized. After confirming eligibility and reviewing the consent, eligible women will sign the consent using an IRB approved e-consent platform. After consent is attained, participants will be given a study number. Then baseline questionnaires will be completed, women will be randomized to vulvovaginal treatment with hypnosis starting in two weeks or vulvovaginal treatment control. Randomization will be done at the time of consent using a random number generator with “1” being the intervention group and “2” being the control group. They will then be educated about treatment with a vaginal moisturizer (see intervention details below). This treatment will begin within two weeks of completing the baseline visit (to allow for shipping of the moisturizer) and will be verified with the study coordinator. The start of vulvovaginal treatment will be confirmed by the study coordinator either through an email or phone communication with the participant. After confirmation of the start of vaginal moisturizer treatment, behavior education visit (Intervention) or follow up phone call (Control) will be planned for two weeks (+/- 3 days) for both groups.

Behavioral education visit: After treatment for vulvovaginal dryness has been underway for two weeks for the intervention group and VVA control group, a second remote visit will be conducted to assess how the vaginal treatment is progressing and to answer any questions about use of the moisturizer and assess for any adverse events. Also, during this second remote visit, the intervention group will be educated about the hypnotic induction intervention (see intervention information below). The rationale for splitting this education into a second visit is two-fold. First, doing it during the baseline visit would make that visit too long and too complex. It is likely participants would be overwhelmed with all of the information. Secondly, since the treatment for vulvovaginal

atrophy will take eight weeks for large effects to be seen, it is important the treatment get started and women get into that routine before adding a behavioral component. It is a standard approach in complex behavioral change to take a stepwise approach.

Phone follow up calls: Participants in both groups will have follow-up calls every two weeks (+/- 3 days) during the intervention except the week of the behavioral education visit to assess for adverse events, problem solve any lack of adherence, ensure completion of data collection and enhance study engagement.

A Screening and Enrollment Log will be maintained to document eligibility/ineligibility, screen dates, consent dates, and referral source of each individual screened.

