1.0 Objectives/Specific Aims

Primary Aim: Evaluate the feasibility and acceptability of a multi-component intervention for sexual function.

Hypothesis: At least 80% of randomized participants will complete the study without differential withdraws from the VVA control group.

Exploratory Aims:

Aim 2: Determine which measure (FSFI, ITS or PROMIS SexF) should be the primary outcome for this multi-component intervention for a larger, well powered randomized trial.

Aim 3: Determine the effect size to be able to adequately power a larger randomized trial.

This study is related to an NCI Moonshot priority (F) to minimize the debilitating side effects of cancer treatment. Completion of these aims will provide a critical foundation for NCI Cancer Prevention and Control Clinical Trials Grant Program R01 submission to implement a phase II or III randomized trial to implement in the NCORP network.

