Effect sizes, Cohen's *d* or *f*, will be calculated for from baseline to week 8. Effect sizes will be calculated for both study arms for the PROMIS, FSFI total score; FSFI lubrication, pain, and desire subscales and the Impact of Treatment Scale. Means, variance, and 95% confidence intervals will also be calculated to better estimate what sample size is needed for a larger trial with at least 80% power to detect at least a medium effect size.

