7.2 Power Considerations

Since this is a feasibility study our main outcome is to assess accrual, retention, attrition, measure sensitivity, and effect size for the multi-component intervention. A sample of 15 participants per arm will allow us to design estimates that we can use for the development of a larger study.

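### Allocation is described only as a 1-or-2 random draw for each woman, which does not guarantee the planned 15 per arm, and no concealment or locked record is described

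*Combined protocol and SAP*

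**What the plan says.** The only account of allocation is in section 4.2, under the baseline visit: "Randomization will be done at the time of consent using a random number generator", where 1 denotes the intervention group and 2 the control group. The sentence just before it reads "Then baseline questionnaires will be completed, women will be randomized to vulvovaginal treatment with hypnosis starting in two weeks or vulvovaginal treatment control".

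Section 4.1 describes the study in these words: "This will be a randomized two arm trial to evaluate the feasibility and acceptability (attrition), and effect size". Section 7.2 sets the size: "A sample of 15 participants per arm will allow us to design estimates that we can use for the development of a larger study".

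Three parts of the plan depend on the arms that result:

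- the primary hypothesis in section 1.0: "At least 80% of randomized participants will complete the study without differential withdraws from the VVA control group";
- the effect sizes under Aim 3 in section 7.1: "Effect sizes will be calculated for both study arms for the PROMIS, FSFI total score";
- the audio part of the adherence criterion (item h in section 5.0, used in the section 7.1 feasibility rule), which on study only hypnosis-arm women can inform.

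The text reviewed states no allocation ratio, blocking, prepared list or concealment method. It does not say who operates the generator or how a result is fixed once drawn. The Screening and Enrollment Log in section 4.2 covers eligibility, screening and consent dates and referral source. Allocation is not among its listed contents.

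**The concern.** A generator run for each woman at her visit and returning 1 or 2 is, on its plain reading, simple randomization. Arm sizes are then left to chance, while section 7.2 treats 15 per arm as given. Nothing in the plan connects the two.

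The second issue is protection of the draw. Eligibility confirmation, consent and randomization all happen in one visit, and the plan does not say that a result is recorded once and cannot be replaced. Only one arm is taught hypnosis, so women know their arm, and the outcomes are self-reported. Sound allocation is therefore one of the few safeguards available.

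The third issue is timing. If the draw really takes place at consent, women could complete the baseline questionnaires knowing their arm. The baseline values feed every change score under Aims 2 and 3.

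**Working it through.** **Inputs.** Two arms (section 4.1); 15 per arm, hence 2 × 15 = 30 women (section 7.2); codes 1 and 2 (section 4.2). Equal probability and independence of draws are assumptions, since no ratio is stated.

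**The plan's own figure.** The 15 per arm comes with no alpha, power, effect size or precision target, so there is no calculation to reproduce. The 80% power and medium effect in section 7.1 refer to the future trial. What can be checked is whether the stated method yields the stated arms.

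**Arm sizes.** Let X be the number in one arm, X ~ Binomial(30, 0.5).

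P(15/15) = C(30,15)/2^30 = 155,117,520/1,073,741,824 = 0.144, so the split differs from 15/15 in 1 − 0.144 = 0.856 of trials.

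For k > 15, P(k/(30−k) or worse, either direction) = 2 × P(X ≥ k).

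**Precision.** The standard error of a standardized between-arm difference is sqrt(1/n1 + 1/n2). At 15/15 it is sqrt(2/15) = 0.365. At 18/12 it is sqrt(1/18 + 1/12) = 0.373, ratio 1.021. At 20/10 it is sqrt(1/20 + 1/10) = 0.387, ratio 1.061. The 95% half-width is 1.96 times the standard error.

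| Split | Probability of this or worse | SE relative to 15/15 | 95% half-width |
|---|---|---|---|
| 15/15 | (exact split: 14.4%) | 1.000 | 0.72 |
| 18/12 | 36.2% | 1.021 | 0.73 |
| 19/11 | 20.0% | 1.038 | 0.74 |
| 20/10 | 9.9% | 1.061 | 0.76 |
| 21/9 | 4.3% | 1.091 | 0.78 |

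The mean absolute difference between arms is 4.3 women. The chance that the hypnosis arm in particular has ten or fewer is half of 9.9%, about 4.9%. In an arm of 10, each woman moves a retention or adherence rate by 1/10 = 10 points, against 1/15 = 6.7 points in an arm of 15.

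**If simple draws were kept.** For both arms to reach 15, total enrolment would need to be 37 for a probability of 0.81, 40 for 0.92, or 42 for 0.96.

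**Under a restricted sequence.** Three blocks of 4 and three of 6 give 12 + 18 = 30 women and 6 + 9 = 15 per arm. Within a balanced block of 6 the arms can differ by at most 3, so even an early stop leaves a difference of no more than 3.

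**Timing, side by side.** Section 4.2 first lists consent, baseline questionnaires and randomization in that order, and the sentence quoted above repeats that order. The next sentence puts the draw at the time of consent, which precedes the questionnaires. Both cannot be literally true.

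**The case against.** The strongest reply is that much of this rests on silence. A random number generator can also produce a blocked list, and the plan never says that the draw is unrestricted. Some parts of the document were not in the text reviewed. This stands to the extent that the finding must be worded as restriction and concealment not being described.

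The reply also has force on size. The loss of precision is small, section 7.2 sets no target that it would breach, and the section 7.1 thresholds for accrual, retention and adherence are not stated by arm. Overall accrual and retention do not depend on the split. Section 7.1 describes effect sizes for both arms without naming a between-arm estimator. Differential withdrawal does compare the arms, but it would be imprecise even at 15 against 15.

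A reader might infer more than the documents support:

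- *Enrolling staff can see or repeat the draw.* The plan does not say who runs it or that it may be repeated. It only fails to exclude an unlogged redraw.
- *Enrolment could be delayed to obtain a preferred arm.* Independent draws made at the visit cannot be predicted, so delay gains nothing. A result seen only after consent cannot alter that woman's eligibility or consent.
- *The hypnosis arm would tend to be the short one.* Under equal probability either arm is equally likely to be smaller.
- *The trial cannot reach 15 per arm.* It can; the method does not guarantee it.

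Finally, blocking brings its own weakness. In an open trial, staff who track assignments may guess the end of a block, particularly with small blocks. That bears on the choice of block sizes. It does not justify leaving the method unspecified.

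**Conclusion.** The point holds in a limited form. On its plain reading, the stated method misses the stated 15/15 split about 86% of the time and gives 18/12 or worse about 36% of the time. The cost in precision is roughly 2% to 6% in standard error at 18/12 to 20/10. The practical effect is more visible in rates for a single arm, where each woman may carry 10 points instead of 6.7. These figures assume 30 independent, equal-probability draws.

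The risk from an unprotected draw cannot be quantified from the documents. The timing contradiction is in the text itself and needs reconciling whichever method is used. None of this defeats the feasibility aim, but it should be corrected, because the study is meant to support a larger randomized trial and its allocation procedure should be reproducible.

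**What to change.** Replace the sentence on randomization in section 4.2 with wording to this effect:

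> Allocation is 1:1. A sequence totalling 15 per arm is generated before the first enrolment by a team member who does not enrol participants, using randomly ordered permuted blocks of varying size that are not disclosed to enrolling staff (for example 4 and 6, summing to 30). The sequence is held in the data platform or, if paper is used, in sequentially numbered sealed envelopes. Each assignment is released and logged once, only after consent and the baseline questionnaires are recorded. No assignment is redrawn.

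This also settles the timing conflict. Add the allocation and its date to the Screening and Enrollment Log.

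The cost is one paragraph and a short setup task, with no extra participants. Someone outside enrolment must be named to prepare the list, and the documents do not identify such a person. Section 6.1 names REDCap only as one possible platform and allows paper, hence the envelope alternative. Some end-of-block predictability remains. It is limited by the varying, undisclosed block sizes and by release only after consent and baseline.

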4.3 Subject Selection

This feasibility study will focus on breast cancer survivors because substantial data demonstrates a high prevalence of sexual dysfunction in breast cancer survivors⁸⁻¹⁰ and this population has been found to be helpful in providing feedback about interventions and their experience.^{48,49}

4.3.1. Inclusion Criteria

1. Age \geq 18 female
2. History of breast cancer, stages I, II or III
3. Completed primary treatment (chemotherapy, radiation and/or surgery) \geq 3 months and \leq 5 years prior to registration
4. May use concurrent adjuvant endocrine therapy or HER2-targeted therapy while on study
5. May use topical products (e.g., lidocaine) vaginally prior to penetrative vaginal sex
6. Ability to read and write English
7. Able to engage in sexual activity
8. Currently has a sexual partner
9. Responds “yes” to “Do you currently experience vaginal or vulvar dryness and/or pain with sexual activity?”
10. Responds “yes” to at least one of the following questions:
 - “Have you experienced negative changes in your body image since being diagnosed or treated for cancer?” or
 - “Have you experienced negative changes in your sexual desire since being diagnosed or treated for cancer?”

4.3.2 Exclusion Criteria

1. Antidepressants are allowed if a person has been on them for 30 days prior to registration, and dose or treatment is not expected to change
2. Past history of sexual abuse
3. Psychiatric disorder such as major depressive disorder, bipolar disorder, obsessive compulsive disorder or schizophrenia. (Defined per medical history and/or patient self-report)
4. Currently enrolled in another study that addresses sexual health (enrollment in other clinical trials will be allowed)

5 Use of oral, transdermal or vaginal estrogen is not allowed while on study

4.4 Intervention Group

The entire length of the study intervention will be eight weeks with the first two weeks treating only vulvovaginal dryness and then adding treatment for body image and libido for an additional six weeks while continuing to treat the vulvovaginal atrophy.

Vaginal Moisturizer

Vulvovaginal dryness will be treated with a daily moisturizer for two weeks, then every other day for the remaining six weeks. Vaginal moisturizer will be applied at night, before sleep and after all sexual activity. Several moisturizers are available, including vaginal DHEA (IntraRosa®). Due to the need for reproducibility, we have decided to use one non-hormonal vaginal moisturizer, Replens™ moisture, which is a vaginal moisturizer consisting primarily of a purified water, glycerin, and mineral oil. Other ingredients included in the formulation are polycarbophil, carbomer, homopolymer type B, hydrogenated palm oil glyceride, sorbic acid, sodium hydroxide. The moisturizing gel was determined to be a medical device for marketing by the FDA in 2010. It has been studied in limited populations^{50,51} and shown to have efficacy in treating vulvovaginal atrophy. It is non-hormonal (unlike vaginal DHEA) and therefore will be more likely to be acceptable by a broader range of oncology providers.

Hypnotic Relaxation Intervention: a behavioral treatment for body image and libido

The hypnotic relaxation intervention consists of three different audio files. Each audio file will be used 3 times per week for 2-weeks. These three hypnotic inductions build upon each other. Each hypnotic induction is about 20 minutes in length. The first hypnotic induction audio consists of focusing on relaxation, feelings of wellness, wholeness, strength, and confidence. The second hypnotic induction audio focuses more specifically on body image related to sexuality and being a sexual being. The third hypnotic induction audio focuses on sexual desire, passion, and energy.

Audio I: Hypnotic relaxation for deepening relaxation and a sense of well being

Perform a hypnotic induction to address self-love and enhance relationship to self; experience deep relaxation and suggestions for a sense of wellbeing. Used during study weeks 3 and 4.

Goals:

- Experience an increased sense of relaxation
- Experience improved feelings about their body
- Experience feelings of comfort and well being

Audio II: Hypnotic Relaxation for Improving Self Image Awareness

Perform a hypnotic induction to focus on improving body-image; suggestions for visualizing a body as strong, healthy, and beautiful. Used during study weeks 5 and 6.

Goals:

- Increase relaxation

- Build on positive feelings about your body
- Improve feelings about your sexuality
- Improve sexual experience

Audio III: Hypnotic relaxation for sexual desire and energy

Perform a hypnotic induction to improve desire for intimacy and experience increased energy and sense of wellbeing. Used during study weeks 7 and 8.

Goals:

- Increase relaxation
- Build upon improved feelings about your body
- Build upon improved feelings about your sexuality
- Improve sexual desire and energy

VVA Control

The VVA control group will get the eight weeks of vaginal moisturizer exactly as described above for the intervention group. After completion of the eight weeks of the study, the women assigned to the VVA control will be offered the Hypnotic Relaxation Intervention to complete on their own off study.

Accrual: Our research team has successfully recruited cancer survivors into clinical trials with an average of 4-6 per month. Weekly and monthly accrual goals will be set and achieved through a multipronged recruitment approach.

4.5 Time and Events Table

Table 2. Schedule of Participant Activities (All study contact is virtual)

Activities			Treatment and Assessments							
	Screening	Baseline	Wk 1	Wk 2	Wk 3	Wk 4	Wk 5	Wk 6	Wk 7	Wk 8
Study Education										
Consent										
Screening Check List										
Demographic Information Form										
Outcomes										
Female Sexual Function Index full scale										
FSFI subscales: pain, dryness, desire		Included in full scale								Included in full scale
Impact of Treatment Scale										
PROMIS® Sexual Function and Satisfaction										
Current vaginally applied topical products										
Hypnosis practice log					*	*	*	*	*	*
Adverse Events										
Follow up Phone Calls										
Conditions										
Intervention		Vaginal Moisturizer								
		Hypnosis								
VVA Control		Vaginal Moisturizer								

* Intervention group only

5.0 Measures

Feasibility: We will keep spreadsheets of the numbers of women who receive a full eligibility screen and how many of those are found eligible versus not eligible, and of those eligible, how many consent to participate versus decline participation. The analysis and definition of what is considered feasible is in the statistical analysis section.

Acceptability: We will keep records of the number of women who complete the protocol, including the questionnaires at all data points versus those who do not complete either the protocol treatment, the questionnaires, and/or both. The analysis and definition of what is considered feasible is in the statistical analysis section.

Adherence: We will keep the following data to determine adherence to various aspects of the study: a) Number of missing questions within questionnaires; b) number and type of missing questionnaires; c) number of women who use the moisturizer exactly per protocol; d) number of women who use the moisturizer at least 80% of the time described by the protocol; e) number of women who use the moisturizer less than half of the time described by the protocol; f) number of women in each arm who listen to each audio sessions at least once in the assigned two week period; g) number of women in each arm who listen to each audio session at least once per week; h) number of women in each arm who listen to each audio session more than once per week.

Demographic Information Form: a brief medical history that obtains age, gender, sexual orientation, race/ethnicity, education level, marital status, cancer diagnosis, and similar demographic information. In addition, any other medical conditions that would exclude possible participants will be captured with this form.

Hypnosis Practice Log: Frequency of home practice is thought to be one of the moderators of the efficacy of hypnosis interventions.⁵² Participants in the hypnosis group will be given a log to be completed weekly. The log will provide space to put the date, whether or not the participant listened to their audio recording, the number of times they practiced, and provide a space for comments about any interruptions or barriers to listening to the recordings.

Current topical (e.g. lidocaine or vaginal moisturizer) products will ask which products (if any) participants used vaginally within the last 2 weeks.

Female Sexual Function Index is a relatively brief measure (19 items) that has been developed and validated to be used across the age range of women, including postmenopausal women.⁵³ Its conceptualization came out of an evolving understanding of female sexual functioning in recent years. It is a multi-dimensional measure that covers the major domains of female sexual functioning including desire, arousal, satisfaction, and orgasm. Additionally, it addresses lubrication and pain. Its discriminant validity is based on its ability to differentiate women diagnosed with female sexual arousal disorder from normal controls. The FSFI looks at measures of both frequency and desire in each domain as well as satisfaction in most domains. The desire subscale consists of two items and has a range of 1.2 to 6 when scored. A cut off for less than normal desire has been determined to be less than 3.3. The FSFI has been used in both intervention and epidemiologic studies. The FSFI has been validated across a wide range of sexual problems, with the most recent Cronbach alpha's being over 0.9 for internal reliability. A score of 26.55 (from a range of 2 to 36) was found to be the cut point to distinguish women with and without sexual dysfunction (lower scores indicating sexual dysfunction). The FSFI was

used in the Alliance N10C1 study that accrued mostly women with breast cancer.⁵⁴

Impact of Treatment Scale is a measure of body change stress and was developed by investigators at The Ohio State University. It was developed and tested specifically in women with breast cancer. It has demonstrated good reliability and validity in both samples, with Cronbach alphas over 0.90. It was able to discriminate between women with lower and higher satisfaction with their sexual life.⁴⁴

PROMIS® Sexual Function and Satisfaction V2.0 (PROMIS SexF V2) measures sexual activities, symptoms, functioning, and evaluation of sexual experiences.⁵⁵ General screener items ask about sexual activity and reasons for not having sexual activity in the past 30 days. Researchers are encouraged to select the sexual function and satisfaction domains and items that are relevant to the specific sample being studied. Participants will answer the 14-item version that includes screener items, items asking about interest in sexual activity, lubrication, vaginal discomfort, clitoral discomfort, labial discomfort, orgasm and pleasure, and satisfaction. In this instrument, higher scores indicate more of the thing being described by the domain. Reliability and validity have been demonstrated in multiple studies. In the validation study, Cronbach's alpha scores ranged from 0.85 to 0.98.⁵⁵ This measure has been used in other studies of dyadic sexual health interventions with similar reliability and validity.⁵⁶

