7.1 Analysis Plan

Aim 1: Evaluate the feasibility and acceptability of a two-component intervention for sexual function.

Feasibility will be evaluated through determining the accrual rate and screen failures. Acceptability will be determined by retention rates.

Accrual rates will be calculated by determining the number of women per month who consented to participate in the study divided by the number who were eligible and educated about the study.

For purposes of this study, screen failures will be calculated as the number of women for whom full eligibility criteria are evaluated using an eligibility checklist and initial screening call and who are determined to be ineligible through that call.

Retention will be calculated as the number of women who complete all eight weeks of the study and complete the FSFI at baseline and eight weeks divided by the number who are randomized and begin study treatment.

Conversely, attrition rates will be calculated by dividing the number of women who do not provide FSFI endpoint data for all data points by the number of women who are randomized and begin study treatment. Attrition rates of 25% or less will be considered feasible. Withdrawal reasons will be captured and reported by category.

Adherence: Adherence will be determined by calculating the number of women who begin study treatment who have at least an 80% compliance with study treatment related to the vaginal moisturizer and behavioral education materials.

This study will be determined to be feasible and acceptable if we have at least a 60% accrual rate; 80% retention rate and an 80% adherence rate (d+h under adherence).

Aim 2: Determine which measure (FSFI, ITS or PROMISE SexF) should be the primary outcome for this multi-component intervention for a larger, well powered randomized trial.

For all of the patient reported outcome measures, we will calculate missing data rates, change from baseline to each data point, and look at how variable measures are over time. This information, along with effect size data discussed in Aim 3, will be considered in determining the optimal measure to use for the primary outcome in a larger trial.

Criteria we will be looking for in a “winning” measure includes: a lack of missing data on any items; smaller “placebo” response, evidence of a better linear trend over time, and sensitivity to change.

Aim 3: Determine the effect size to be able to adequately power a larger randomized trial.

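### The 80% adherence go criterion scores hypnosis by item h, which is not an 80% rule and misclassifies women in both directions

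*Combined protocol and SAP*

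**What the plan says.** Section 4.4 sets the hypnosis schedule: "The hypnotic relaxation intervention consists of three different audio files", and "Each audio file will be used 3 times per week for 2-weeks". Section 7.1 (Aim 1) defines adherence by counting women who have "at least an 80% compliance with study treatment related to the vaginal moisturizer and behavioral education materials". It then makes adherence one of three conditions for calling the study feasible and acceptable, and says how it is scored: "80% retention rate and an 80% adherence rate (d+h under adherence").

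The two letters point to the adherence list in section 5.0. Item d is "d) number of women who use the moisturizer at least 80% of the time described by the protocol". Item h is "h) number of women in each arm who listen to each audio session more than once per week". Items f and g, the other two audio items, ask for less listening than h. The weekly practice log in the same section records "the number of times they practiced". Section 7.2 gives the size: "A sample of 15 participants per arm".

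**The concern.** Section 7.1 uses 80% twice. One is the compliance each woman must reach; the other is the share of women who must reach it. The conflict is with the first. For the moisturizer, item d carries that per-woman 80%. For hypnosis no listed item does, and the item chosen, h, is a weekly frequency floor below 80% of the schedule.

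The adherence rate is part of the answer to the primary aim. As written, two analysts who both follow section 7.1 could report different hypnosis adherence from the same logs, one using the definition and the other the lettered items. If the choice is made after the logs have been seen, the go decision becomes post hoc. Section 5.0 itself regards practice frequency as a possible moderator of the hypnosis effect, so the adherence figure will matter to readers planning the larger trial.

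**Working it through.** **Inputs.** Three audios, two weeks each, three sessions a week (section 4.4); 80% compliance per woman and an 80% adherence rate (section 7.1); items d and h (section 5.0); 15 women per arm (section 7.2).

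**The stated 80% against item h.**
- Prescribed: 3 × 2 × 3 = 18 sessions, 6 per audio.
- 80% of 18 = 14.4, so at least 15 sessions.
- Item h, counted weekly, needs at least 2 sessions in each of six weeks. The minimum is 6 × 2 = 12, and 12/18 = 66.7%, which is 13.3 points below 80%. The stated 80% is not reproduced.
- Women with 12, 13 or 14 sessions can pass h while below 80%.
- The reverse also occurs: 3+3+3+3+3+1 = 16, and 16/18 = 88.9%, but the last week fails h.

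**Effect on the arm.** The criterion needs 0.8 × 15 = 12 women.
- All 15 at exactly two a week: 15/15 = 100% by h, 0/15 = 0% by 15 of 18.
- Twelve at two a week and three doing none: 12/15 = 80% by h, so the threshold is met, with 12 × 12 = 144 of 15 × 18 = 270 sessions delivered (53.3%). The corresponding floor under 15 of 18 is 12 × 15 = 180 of 270 (66.7%).

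**How often the two rules disagree.** The documents give no completion rate. I assume each session is completed independently with probability p, and vary p from 0.70 to 0.90.
- P(pass h) = [3p²(1−p) + p³]⁶.
- P(15 of 18) = P(X ≥ 15), X binomial with 18 trials and probability p.
- A woman passing h has 12 + k sessions, where k is her number of three-session weeks. So P(pass h, below 80%) = Σ over k = 0, 1, 2 of C(6,k)(p³)ᵏ[3p²(1−p)]⁶⁻ᵏ.
- P(80% but fail h) = P(15 of 18) − [P(pass h) − P(pass h, below 80%)].

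At p = 0.75 both weekly terms equal 0.4219. P(pass h) = 0.84375⁶ = 0.361. P(pass h, below 80%) = (1 + 6 + 15) × 0.421875⁶ = 0.124. P(15 of 18) = 0.306, so P(80% but fail h) = 0.306 − (0.361 − 0.124) = 0.069.

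| p | Pass h | 15 of 18 | Pass h, below 80% | 80%, fail h | Disagree |
|---|---|---|---|---|---|
| 0.70 | 23.2% | 16.5% | 10.8% | 4.1% | 14.9% |
| 0.75 | 36.1% | 30.6% | 12.4% | 6.9% | 19.3% |
| 0.80 | 51.7% | 50.1% | 11.4% | 9.8% | 21.2% |
| 0.85 | 68.7% | 72.0% | 7.8% | 11.1% | 18.9% |
| 0.90 | 84.3% | 90.2% | 3.2% | 9.0% | 12.2% |

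The direction reverses between 0.80 and 0.85. Treating the pass rates as binomial over 15 women, the chance that at least 12 pass is 0.024 by h and 0.018 by 15 of 18 at p = 0.80; 0.26 and 0.36 at p = 0.85; 0.80 and 0.95 at p = 0.90.

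**Overall or per audio.** Applied to each audio, 80% of 6 = 4.8, so 5 of 6 on all three. At p = 0.90 this passes (6 × 0.9⁵ × 0.1 + 0.9⁶)³ = 0.8857³ = 69.5%, against 90.2% for 15 of 18. The two versions are not interchangeable.

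**The case against.** Several objections have force.

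*The sponsor may intend item h.* The lettered items are the specific operational rule. The 80% sentence is general and refers to behavioral education materials, not to audio sessions. Twice a week may be a deliberate choice, and two components need not share a cut-off. This stands as to remedy: the documents do not show which statement governs. It does not remove the conflict, because section 7.1 scores the adherence it has just defined by d and h, and h is an audio item.

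*Item h is not simply lenient.* A reader might infer that h makes it easy to declare an under-dosed arm adherent. The calculation does not support that as a general statement. Where the go criterion is likely to be met (p near 0.90), h passes fewer women than 15 of 18. A wrongly favourable result needs patterned behaviour, such as most women settling at exactly two a week. That is possible, but it is an extreme case.

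*The effect sizes are untouched.* A reader might also infer that the pilot effect size would be presented as coming from women who took 80% of the sessions. Section 7.1 calculates effect sizes for both arms from baseline to week 8, and section 7 describes no adherent subset, so item h selects nobody for that analysis.

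*A looser reading of h is strained.* Read as an average over two weeks, h would pass 3 of 6 sessions (50%). But item f refers to the two-week period while g and h count per week, so the list itself separates the two. I rely on the weekly reading only.

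*Nothing is lost.* The log holds session counts, so either rule can be computed later. This lowers the severity, but not the need to fix the rule in advance.

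**Conclusion.** The point holds as an inconsistency between a definition and its scoring rule. Section 7.1 promises 80% compliance per woman; item h delivers a weekly floor that passes at 67% of the schedule and can fail a woman at 89%. The fixed-pattern counts follow from the plan's own numbers. The 12% to 21% disagreement and its change of direction rest on my assumption of independent sessions with a common completion probability of 0.70 to 0.90; real listening patterns may differ.

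This should be fixed, but it does not undermine the trial. It affects the hypnosis part of one of three feasibility criteria in a pilot of 15 per arm, and leaves randomization, safety and the effect-size analysis alone. How d and h are combined, what the denominator is, and why h is counted in each arm when controls receive no hypnosis on study are separate questions.

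**What to change.** Before adherence is analysed, reconcile sections 4.4, 5.0 and 7.1 so that the go criterion uses one hypnosis scoring rule.

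- To keep the stated 80% definition: score a woman as adherent to hypnosis if the weekly log shows at least 80% of all prescribed sessions, that is at least 15 of 18 overall. This parallels item d. Keep items f, g and h as descriptive summaries. Name the overall rule explicitly, since a per-audio version gives a different rate.
- If item h is the intended rule: reword section 7.1 so that it no longer describes hypnosis adherence as 80% compliance.

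Either way the prescribed listening frequency is unchanged; only the scoring is at issue. The cost is one sentence and no new data. The reported adherence rate may move up or down.
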